### 1.3 Rationale for the Proposed Study

We hypothesize that standard concurrent chemoradiation in combination with priming, concurrent, and adjuvant nivolumab will improve the feasibility of treatment completion by allowing completion of a regimen that is highly effective but more tolerable than the current standard of care.

This study will begin with a run-in phase to establish the basic feasibility of the nivolumab schedule and determine the MTD (maximally tolerated dose) schedule. This will be followed by an expansion phase which will more rigorously test the feasibility of completion of all therapy as compared to the standard of care.

Furthermore, the design of this trial will allow us to perform immunologic analyses on tumor and peripheral blood specimens pre-treatment and after exposure to nivolumab, chemoradiation-nivolumab, and adjuvant nivolumab. This will allow us to investigate possible future patient specific selection criteria for this regimen and correlate mechanisms of incomplete response to immunologic predictors, which may allow for design of more advanced rational therapies for patients at high risk of distant metastasis.

## 1.4 Correlative Studies

### 1.4.1 PD-L1 immunohistochemistry

In a study of 119 patients with histological diagnosis of NPC from a cancer registry in Thailand, PD-1 and PD-L1 expression were characterized using immunohistochemistry staining on formalin-fixed, paraffin-embedded tumor samples. PD-L1 expression was defined by using a cut-off of  $\geq 1\%$  ( $\geq 1\%-1+$ ,  $10\%-49\%-2+$ ,  $\geq 50\%-3+$ ). PD-L1 was found to be positive in 72% (13% IHC 3+). PD1+ was observed in 11% of patients. Most patients in this study had EBER+ tumors (96%) indicating EBV-related etiology.

In another study from China, co-expression of PD-1 and PD-L1 was found to correlate to poor outcome in NPC treated with standard chemoradiation. Formalin-fixed, paraffin-embedded tissue biopsies from 139 patients treated with conventional chemoradiotherapy were studied. By immunohistochemistry, expressions of PD-1 on tumor-infiltrating lymphocyte and PD-L1 on tumor tissue were detected. The staining results were evaluated with H-score. 52 of these 139 tumors (37.4%) were PD-1+. PD-L1 expression was detected in 132 patients (95.0%) on tumor tissue. High expression of PD-L1 (median H-score  $>35$ ) in tumor tissue significantly correlated with a poor prognosis of disease-free survival ( $P = 0.009$ ). Co-expression of PD-1 and PD-L1 in NPC at diagnosis correlated with the poorest prognosis of disease-free survival ( $P = 0.038$ ).

The DAKO PD-L1 IHC 28-8 pharmDxTM test was recently FDA-approved as a complementary diagnostic test to help physicians determine which patients may benefit most with nivolumab. By using immunohistochemistry staining, expression of PD-L1 on tumor tissue will be detected. The staining results will be evaluated with H-score. The correlation between PD-L1 expression and clinical response will be analyzed. We hypothesize that upregulated PD-L1 expression that persists after two weeks of treatment with nivolumab will be predictive of poor clinical response, but patients who show lower PD-L1 expression at the time of rebiopsy will show an improved clinical response.

### 1.4.2 EBV DNA

Pre-treatment EBV DNA in plasma has been proven to correlate with cancer stage, clinical outcome, and prognosis in patients with endemic NPC. However, post-radiation plasma EBV DNA has an even better correlation with prognosis and has been used to monitor recurrence after definitive therapy. Rising post-treatment plasma EBV DNA has been shown to predate clinical recurrence by 3 to 7 months. Undetectable levels of plasma EBV DNA are observed in patients who remained in remission.

In a large ( $n=170$ ) NPC study in which most patients were treated uniformly with definitive RT (with only 15 patients also receiving weekly CDDP at  $40\text{mg}/\text{m}^2$  during RT), the levels of post-treatment plasma EBV DNA strongly predicted for progression-free survival (PFS) ( $p<0.001$ ) and OS ( $p<0.001$ ), and this post-treatment EBV DNA dominated the effect of pre-treatment EBV DNA. The 1-year PFS was 93% among patients with post-treatment EBV DNA  $\leq 500$  copies/mL, and 48% for those with  $> 500$  copies/mL.

A quantitative plasma EBV DNA assay was developed as an international harmonization study to facilitate EBV biomarker trials. Post-harmonization, the intraclass correlations for each site compared to the index site were 0.83 (0.5-0.95), 0.95 (0.83-0.99) and 0.96 (0.86-0.99),

respectively. The centers in this study will use an assay harmonized among the participating sites.

## **2 Objectives of the Study**

### **2.1 Primary**

- To establish the feasibility of treatment completion of a combined chemoradiation-nivolumab regimen followed by adjuvant nivolumab.

### **2.2 Secondary**

- To determine the clinical response as judged by the investigator;
- To determine the overall response rate at 1 year from completion of therapy, as determined by RECIST 1.1 criteria;
- To determine the locoregional control rate at 1 year post-treatment;
- To determine the distant metastasis rate at 1 year post-treatment;
- ;
- To determine the rate of EBV DNA clearance at end of chemoradiation and at 1 year post-treatment;
- To determine the acute and late toxicity rates according to CTCAE v5.0, including immune-related adverse events (AEs);
- To assess patients' quality of life from baseline through 1 year post-treatment

### **2.3 Exploratory Objectives, Other Assessments**

- To determine the overall survival rate at 5 year post-treatment
- To determine whether PDL1-positive immunohistochemistry and novel quantitative assays correlate to clinical outcome;
- To determine if the density of infiltrating CD3+ T cells/µm^2 correlates to clinical outcome;
- To monitor immune changes by flow cytometry in the circulating T cell response to EBV antigens;
- To compare the change in the circulating T-cell repertoire by TCR sequencing and single-cell T-cell profiling;
- To quantify treatment-induced changes over time in the circulating T cell immune response to EBV using TCR sequencing and enzyme-linked immunospot (ELISPOT) assays.

### **2.4 Endpoints**

#### **2.4.1 Primary Endpoints**

- The primary endpoint will be the rate of completion of adjuvant immunotherapy, in comparison to the rate of completion of a standard adjuvant cisplatin-based platform (historical control). This will be determined based on the ability to complete all prescribed concurrent and/or adjuvant nivolumab without discontinuation for disease progression or toxicity.

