Duration of Therapy	Patients will receive 23 weeks of an anticipated total therapy course, although the duration for an individual patient may be extended to as long as 33 weeks to allow for resolution of toxicities.
Duration of Follow-up	Follow-up visits will occur at 1, 3, 6, 9, and 12 months for up to 12 months after end of treatment. Survival follow-up information may be collected via telephone calls or medical records review for an additional 4 years . Survival and disease status will be collected during this 5-year period until participant death, withdrawal, or if the participant is lost to follow-up.
Duration of study	The study will reach completion in 6 years from the time the study opens to accrual.
Study Drugs	Nivolumab will be administered intravenously, at a dose of 240 mg every 14 days. Nivolumab may be held for toxicity but there are no dose reductions.
Safety Assessments	Analyses will be performed for all patients having received at least one dose of study drug. The study will use the CTCAE v5.0 for reporting of non-hematologic adverse events and modified criteria for immune related adverse events. Safety assessments will consist of monitoring and reporting adverse events (AEs) and serious adverse events (SAEs) that are considered related to nivolumab, all events of death, and any study specific issue of concern. The study period during which all AEs and SAEs must be reported begins after informed consent is obtained and study treatment is initiated and ends 12 months following the last administration of study treatment or study discontinuation/termination, whichever is earlier.
Efficacy Assessments	The primary measure of feasibility will be the rate of completion of all adjuvant therapy. This will be determined based on ability to complete all 6 cycles of adjuvant nivolumab without discontinuation for disease progression or toxicity. Secondary measures of efficacy will be clinical response as judged by the investigator; ORR by RECIST 1.1; locoregional control rate, distant metastasis rate, overall survival rate determined by standard physical examination and radiologic imaging; the rate of EBV DNA clearance at end-chemoradiation and at 1 year post-treatment as determined by PCR assay; toxicity assessments graded by CTCAE v5.0 and modified immune related criteria; and quality of life by FACT-NP, FACT-Taxane, HHIE-S, and EuroQOL EQ-5D-3L. Exploratory assessments are self-explanatory.

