The very pressing question of whether there is any oncologic benefit to be accrued from the use of adjuvant chemotherapy in locoregionally advanced NPC was studied in a recent randomized trial from China. This phase III study compared RT with weekly CDDP followed either by 3 cycles of CDDP/5-FU or no adjuvant treatment. In 508 patients, the study found no statistically significant improvement in either progression-free or overall survival from the addition of adjuvant cytotoxic chemotherapy. Of note, in this study, 82% of patients assigned to the arm receiving weekly cisplatin plus adjuvant cisplatin-5FU started adjuvant chemotherapy, but only 63% were able to complete all 3 adjuvant cycles (52% therefore started and completed all adjuvant therapy). During adjuvant chemotherapy, 42% of patients experienced grade 3-4 toxic effects; 49% had dose reductions and 69% experienced delays in treatment. This is notable given that there was no apparent increase in rates of completion or better tolerance compared to results from the earlier era.

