**Criteria to Resume Nivolumab**

Patients may resume treatment with nivolumab when the drug-related AE(s) resolve to the grade specified in the tables above and as detailed in Appendix 5.

If the criteria to resume treatment are met, the patient should restart treatment at the next scheduled time point (two-week interval) per the protocol.

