### 8.2.2 Run-in phase

Six patients will be enrolled for the initial run-in phase, with nivolumab dosing of 240 mg. Enrollment will cease until all 6 patients have completed concurrent chemoradiation and nivolumab. If 3 or more of the first 6 patients experience grade 3-4 immune related toxicity or other DLT during concurrent chemoradiation and nivolumab therapy, then the run-in will restart at dose schedule 2 with 6 additional patients. In dose schedule 2, patients will start nivolumab

concurrent with chemoradiation and will not start nivolumab prior to chemoradiation. If 3 or more of the first 6 patients experience grade 3-4 immune related toxicity or other DLT during concurrent chemoradiation and nivolumab at dose schedule 2, then the dose schedule will be changed to dose schedule 3 and the run-in will restart at dose schedule 3 with 6 additional patients. In dose schedule 3, patients will start nivolumab in the adjuvant phase only and will not receive nivolumab before or during chemoradiation, and the toxicity of nivolumab will be assessed during the adjuvant phase. No dose escalation or reduction will be allowed in the run-in phase. Dose modifications of nivolumab are not permitted from the standard dose of 240 mg every 14 days.

The run-in will cease when 4 or more patients have completed chemoradiation and nivolumab therapy at the same nivolumab dose schedule without experiencing grade 3-4 toxicity or other DLT (this will be considered the maximally tolerated dose), or alternatively, if 3/6 patients have experienced grade 3-4 toxicity at dose schedule 3 during administration of adjuvant nivolumab (in which case the entire study will terminate). Therefore, a minimum of 6 patients and a maximum of 18 patients will be enrolled in the run-in phase.

DLT criteria are grade  $\geq 3$  immune-related adverse events, need to hold nivolumab for  $>28$  days due to toxicity, and for patients receiving concurrent nivolumab with chemoradiation, inability to complete chemoradiation or need to hold chemoradiation for  $>3$  days due to immune-related toxicity.

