### **8.2.5 Replacement Policy**

A maximum of 40 evaluable patients will be enrolled in the study using a Simon's two-stage design for the primary endpoint. An evaluable patient will be defined as one who receives any amount of study drug. If a patient drops out of the study before receiving nivolumab, a replacement patient will be allowed.

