## **8.4 Analysis Plans**

### **8.4.1 Analysis Population**

Primary endpoint will be determined in patients who receive the study drug for a minimum of 1 cycle (or 14 days) at the MTD schedule.

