### **8.4.2 Primary Analysis (or Analysis of Primary Endpoints)**

Rate of completion of all adjuvant immunotherapy is defined as completion of all post-chemoradiation cycles of nivolumab, per protocol.

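### Under dose schedule 3 the plan leaves out patients who never start adjuvant nivolumab, although the 52% benchmark counts such patients as failures; separately, section 2.4.1 words the endpoint differently from section 8.4.2

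*Combined protocol and SAP*

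**What the plan says.** **Denominator.** Section 8.4.1 determines the primary endpoint in "patients who receive the study drug for a minimum of 1 cycle (or 14 days) at the MTD schedule". Section 8.2.5 calls a patient evaluable after any amount of study drug and adds: "If a patient drops out of the study before receiving nivolumab, a replacement patient will be allowed". Under dose schedule 3, section 8.2.2 states that "patients will start nivolumab in the adjuvant phase only and will not receive nivolumab before or during chemoradiation"; the schedule 3 schema in section 3.2 agrees.

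**Benchmark.** Sections 8.1.1 and 8.2.3 compare the completion rate with a historical 52%. Section 1.1.2 shows its origin. In the randomised trial of adjuvant cisplatin-5FU, 82% of patients assigned to the adjuvant arm started it, but "only 63% were able to complete all 3 adjuvant cycles (52% therefore started and completed all adjuvant therapy").

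**Decision rule.** Section 8.2.1 has 22 patients in stage 1 (stop at 11 or fewer completions) and rejects at 26 or more of 40. Section 8.2.4 has 15 in stage 1 (stop at 7 or fewer) and rejects at 18 or more of 28. Both set a null of 0.50 against 0.70. Which design applies is a separate matter, so results are given for both.

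**Numerator.** Section 2.4.1 first names adjuvant completion as the endpoint, then judges it by "ability to complete all prescribed concurrent and/or adjuvant nivolumab without discontinuation for disease progression or toxicity". Section 8.4.2 has it "defined as completion of all post-chemoradiation cycles of nivolumab, per protocol", and the Abstract (Efficacy Assessments) uses "ability to complete all 6 cycles of adjuvant nivolumab without discontinuation for disease progression or toxicity".

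**The concern.** The primary result is a count of completers against a fixed threshold, so who is in the denominator and who counts as a completer decide it.

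The main problem is confined to schedule 3. A patient there who goes through chemoradiation but never starts adjuvant nivolumab has received no nivolumab. That patient falls outside the section 8.4.1 population and, on dropping out, may be replaced. The trial would then set a rate among starters against a benchmark whose base is everyone assigned. The error favours nivolumab: a regimen no better than the benchmark passes more often than the design intends.

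The smaller problem concerns schedules 1 and 2. After a hold, "the patient should restart treatment at the next scheduled time point (two-week interval) per the protocol", so a concurrent dose can be missed. A patient who misses one and then receives all 6 adjuvant doses is a completer under the Abstract and section 8.4.2. On a strict reading of section 2.4.1, the same patient could be scored a failure.

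**Working it through.** **Method.** With stage 1 size n1, futility bound r1, total n and rejection count r, the exact rejection probability at true rate p is the sum, over x from r1 + 1 to n1, of P(Bin(n1, p) = x) × P(Bin(n − n1, p) ≥ r − x).

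**1. The plan's own figures.**

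| True rate | 26/40 rule | 18/28 rule |
|---|---|---|
| 0.50 | 0.0396 | 0.0900 |
| 0.52 | 0.0664 | 0.1294 |
| 0.70 | 0.8028 | 0.8009 |

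The stated errors (at most 0.05; 0.09) and the power of 80% reproduce. The 0.52 row is the correct comparator below, because it is the rate of a regimen exactly equal to the benchmark with everyone counted.

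**2. What the 52% contains.** 0.82 × 0.63 = 0.5166, which rounds to 52%. The 63% is therefore a rate among starters, and the 52% treats non-starters as failures.

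**3. Effect of dropping non-starters under schedule 3.** If the all-patient rate is 0.52 and a fraction s start adjuvant therapy, the rate among starters is 0.52 / s.

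| s | Source | 0.52 / s | 26/40 rule | 18/28 rule |
|---|---|---|---|---|
| 100% | non-starters counted, or none | 0.5200 | 0.0664 | 0.1294 |
| 95% | assumed | 0.5474 | 0.1236 | 0.2006 |
| 90% | assumed | 0.5778 | 0.2203 | 0.3030 |
| 82% | section 1.1.2, cisplatin-5FU | 0.6341 | 0.4832 | 0.5381 |

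**4. How often this branch yields a primary analysis.** Schedules 1 and 2 must each show 3 or more DLTs in 6 patients, and schedule 3 must not, since sections 3.3 and 8.2.2 end the study if it does. With an assumed common per-patient DLT rate d and T = P(Bin(6, d) ≥ 3), the probability is T² × (1 − T):

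- d = 20%: 0.0989² × 0.9011 = 0.009
- d = 33%: 0.3130² × 0.6870 = 0.067
- d = 50%: 0.6562² × 0.3438 = 0.148

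**5. Schedules 1 and 2.** Nivolumab is given before or during chemoradiation, so a patient who never reaches the adjuvant phase has normally already had at least one cycle. That patient stays in the denominator as a failure, as in the benchmark.

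**6. Numerator wording.** A patient permanently stopped in the concurrent phase fails under every definition. Only the patient with a missed concurrent dose and full adjuvant treatment can be scored differently.

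**The case against.** **On the denominator.** The exclusion depends on what study drug means. Table 5.1 lists radiation and cisplatin under that heading, and section 5.2.2 uses the term while discussing cisplatin. On that reading a schedule 3 patient would enter the analysis population during chemoradiation. However, the Abstract names only nivolumab as study drug, and the replacement sentence in section 8.2.5 is tied to nivolumab, so the narrower meaning is the better one. What stands is that the term is ambiguous and needs fixing. Replacement is also permissive and applies to patients who drop out of the study, but the section 8.4.1 exclusion operates without it.

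**On likelihood.** A reader might take the chance of reaching schedule 3 (T² = 0.01, 0.10 or 0.43) as the chance that the problem bites. That overstates it, because a failed schedule 3 run-in ends the study with no primary test. The DLT rates are assumed. The 13.1% grade 3/4 rate that section 1.2.3.1 gives for nivolumab in squamous head and neck cancer is only indicative here, but would put the chance near 0.001. The 82% start rate belongs to cisplatin-5FU and need not carry over to nivolumab.

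**On the numerator.** A reader might infer that section 2.4.1 costs substantial power: if only 95% or 90% of adjuvant completers had every concurrent dose, 0.70 becomes 0.665 or 0.63 and power under the 26/40 rule falls to 0.64 or 0.46. The documents do not support this as a finding. They give no such percentages. The qualifier in section 2.4.1 concerns discontinuation, which the protocol separates from holding a dose, and *and/or* may simply cover the different schedules. A held-and-resumed patient can therefore still complete. It is also true that sections 1.3, 3.1 and 8.2.1 speak loosely of completing the whole programme. Those are descriptions; section 8.4.2 is the analysis definition.

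**Conclusion.** The point holds in a limited form. If schedule 3 becomes the MTD schedule and study drug means nivolumab, the trial's completion rate and the 52% have different denominators, and the difference favours nivolumab. For a regimen equal to the benchmark, the rejection probability rises from 0.07 to between 0.12 and 0.48 under the 26/40 rule, and from 0.13 to between 0.20 and 0.54 under the 18/28 rule. These ranges rest on start rates of 95% to 82%, of which only the 82% is documented, and for a different adjuvant drug. The branch itself has probability of about 0.01 to 0.15 at common DLT rates of 20% to 50%. It is nevertheless a pre-specified path, so its denominator should be pre-specified too.

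A reader might infer that the comparison with 52% is biased throughout. It is not: under schedules 1 and 2 adjuvant non-starters already count as failures.

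The mismatch between section 2.4.1 and section 8.4.2 is real but smaller. It concerns one type of patient and changes the score only on a strict reading. The *any amount* and *at least 1 cycle* populations of sections 8.2.5 and 8.4.1 also differ slightly and can be settled at the same time.

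**What to change.** - **Section 2.4.1:** delete *concurrent and/or*, so that the endpoint matches section 8.4.2 and the Abstract. Report completion of concurrent nivolumab separately, as a descriptive result.
- **Sections 8.2.5 and 8.4.1:** state that study drug means nivolumab, and use one evaluable population: every patient who receives any nivolumab at the MTD schedule and, under schedule 3, every enrolled patient who starts protocol chemoradiation.
- **Same sections, schedule 3:** state that a patient who starts chemoradiation but never starts adjuvant nivolumab is a non-completion and is not replaced.

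This brings the denominator as close as practicable to the benchmark's base. The match is approximate, because the 52% is a percentage of patients assigned to the arm rather than of those who began chemoradiation.

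The change is wording only, with no new data, sample size or threshold. The cost is a less favourable completion rate under schedule 3. If the planned 70% is an all-patient rate, power stays at 0.80. If it is a rate among starters, counting non-starters gives 0.70 × 0.95 = 0.665 or 0.70 × 0.90 = 0.63, and power under the 26/40 rule of 0.64 or 0.46. The plan should therefore say which rate the 70% is.

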## 2.4.2 Secondary Endpoints

- ORR determined by investigator's assessment and RECIST 1.1 criteria;
- Locoregional control rate;
- Distant metastasis rate;
- Rate of EBV DNA clearance from plasma by standardized PCR assay;
- Treatment-emergent AEs and laboratory abnormalities as determined by National Cancer Institute Common Toxicity Criteria (NCI-CTC) version 4.0 and modified immune related criteria;
- Quality of life as assessed by patient reported outcomes (FACT-NP, FACT-Taxane, HHIE-S, and EuroQOL EQ-5D).

## 2.4.3 Exploratory Endpoints

- Overall survival rate;
- PDL1-positive immunohistochemistry and novel quantitative assays;
- Density of infiltrating CD3+ T cells/ $\mu$ m^2;
- Changes by flow cytometry in the circulating T cell response to EBV antigens;
- Change in the circulating T-cell repertoire by TCR sequencing and single-cell T-cell profiling;
- Changes over time in the circulating T cell immune response to EBV using TCR sequencing and enzyme-linked immunospot (ELISPOT) assays;

